**12.8 Appendix 8. International Working Group Response Criteria for Multiple Myeloma (IMWG-URC)**

Response criteria a	
Standard IMWG response criteria b	
sCR	
 
• CR as defined below AND
 
• Normal FLC ratioc AND
 
• Absence of clonal cells in BM biopsy by immunohistochemistry <math>\kappa/\lambda</math> ratio <math>\leq 4:1</math> or <math>\geq 1:2</math> for <math>\kappa</math> and <math>\lambda</math> patients, respectively, after counting <math>\geq 100</math> plasma cellsd
 

CR	
 
• Negative immunofixation on the serum and urine AND
 
• Disappearance of any soft tissue plasmacytomas AND
 
• <math>< 5\%</math> plasma cells in BM aspirates
 
• In patients with baseline measurable disease only by sFLC, a normal FLC ratio is required
 

VGPR	
 
• Serum and urine M-protein detectable by immunofixation but not on electrophoresis OR
 
• <math>\geq 90\%</math> reduction in serum M-protein plus urine M-protein level <math>< 100</math> mg/24 hours
 
• In patients with baseline measurable disease only by sFLC, a <math>\geq 90\%</math> decrease in the difference between involved and uninvolved FLC levels is required in place of the M-protein criteria.
 
• In patients achieving a VGPR by other criteria, a soft tissue plasmacytoma must decrease by more than 90% in the SPD compared with baseline
 

PR	
 
• <math>\geq 50\%</math> reduction of serum M-protein and reduction in 24-hour urinary M-protein by <math>\geq 90\%</math> or to <math>< 200</math> mg/24 hours
 
• In patients with baseline measurable disease only by sFLC, a <math>\geq 50\%</math> decrease in the difference between involved and uninvolved FLC levels is required in place of the M-protein criteria.
 
• If serum and urine M-protein are unmeasurable, and serum free light assay is also unmeasurable, <math>\geq 50\%</math> reduction in plasma cells is required in place of M-protein, provided baseline BM cell percentage was <math>\geq 30\%</math>.
 
• If present at baseline, a <math>\geq 50\%</math> reduction in the size (SPD)e of soft tissue plasmacytomas is also required.
 

MR	
 
• <math>\geq 25\%</math> but <math>\leq 49\%</math> reduction of serum M-protein and reduction in 24-hr urine M-protein by 50% to 89%
 
• In patients with baseline measurable disease only by sFLC, a <math>\geq 25\%</math> but <math>\leq 49\%</math> decrease in the difference between involved and uninvolved FLC levels is required in place of the M-protein criteria
 
• If present at baseline, a <math>\geq 50\%</math> reduction in the size of soft tissue plasmacytomas (SPD)e is also required.
 

Stable disease	
 
• Not recommended for use as an indicator of response
 
• Stability of disease is best described by providing the time-to-progression estimates
 
• Not meeting criteria for sCR, CR, VGPR, PR, minimal response, or PD
 

Footnotes are defined on last page of this table

Response criteria a	
Standard IMWG response criteria b (Continued)	
PD f,g	
 
• Any 1 or more of the following criteria:           
 
– Increase of 25% from lowest confirmed response value in 1 or more of the following criteria:               
 
– Serum M-protein (absolute increase must be <math>\geq 0.5</math> g/dL);                   
 
○ Serum M-protein increase <math>\geq 1</math> g/dL, if the lowest M component was <math>\geq 5</math> g/dL;
 
○ Urine M-protein (absolute increase must be <math>\geq 200</math> mg/24 hr);
 
○ In patients without measurable serum and urine M-protein levels, the difference between involved and uninvolved FLC levels (absolute increase must be <math>> 10</math> mg/dL);
 
 
 
– In patients without measurable serum and urine M-protein levels and without measurable involved FLC levels, BM plasma-cell percentage irrespective of baseline status (absolute increase must be <math>\geq 10\%</math>);
 
– Appearance of a new lesion(s), <math>\geq 50\%</math> increase from nadir in SPDe of <math>> 1</math> lesion, or <math>\geq 50\%</math> increase in the longest diameter of a previous lesion <math>> 1</math> cm in short axis;
 
– <math>\geq 50\%</math> increase in circulating plasma cells (minimum of 200 cells per <math>\mu\text{L}</math>) if this is the only measure of disease
 
 
 
 
 

IMWG MRD criteria (requires a CR as defined above)	
Sustained MRD-negative	
 
• MRD negativity in the marrow (NGS) and by imaging as defined below, confirmed minimum of 1 year apart.
 
• Subsequent evaluations can be used to further specify the duration of negativity (eg, MRD-negative at 5 years)h
 

Sequencing MRD-negative	
 
• Absence of clonal plasma cells by NGS on BM aspirate in which presence of a clone is defined as less than 2 identical sequencing reads obtained after DNA sequencing of BM aspirates using the LymphoSIGHT platform (or validated equivalent method) with a minimum sensitivity of 1 in <math>10^5</math> nucleated cellsi or higher
 

Imaging plus MRD-negative	
 
• MRD negativity as defined by NGS plus disappearance of every area of increased tracer uptake found at baseline or a preceding PET/CT or decrease to less mediastinal blood pool SUV or decrease to less than that of surrounding normal tissuei
 

Footnotes are defined on last page of this table

ASCT = autologous stem cell transplantation; BM = bone marrow; CR = complete response; CRAB features = calcium elevation, renal failure, anaemia, or lytic bone lesions; CT = computed tomography; FLC = free light chain; IMWG = International Myeloma Working Group; MR = minimal disease; MRD = minimal residual disease; MRI = magnetic resonance imaging; NGS = next generation sequencing; PD = progressive disease; PET = positron emission tomography; PFS = progression-free survival; PR = partial response; sCR = stringent complete response; SPD = sum of the products of the maximal perpendicular diameters of measured lesions; SUV = standardized uptake value; VGPR = very good partial response

a All response categories require 2 consecutive assessments made any time before starting any new therapy; for MRD there is no need for 2 consecutive assessments, but information on MRD after each treatment stage is recommended (eg, after induction, high-dose therapy/ASCT, consolidation, maintenance). MRD tests should be initiated only at the time of suspected CR. All categories of response and MRD require no known evidence of progressive or new bone lesions if radiographic studies were performed. However, radiographic studies are not required to satisfy these response requirements except for the requirement of FDG PET if imaging MRD-negative status is reported.

b Derived from international uniform response criteria for multiple myeloma. Minor response definition and clarifications derived from Rajkumar and colleagues. When the only method to measure disease is by serum FLC levels: CR can be defined as a normal FLC ratio of 0.26 to 1.65 in addition to the CR criteria listed previously. Very good PR in such patients requires a  $\geq 90\%$  decrease in the difference between involved and uninvolved FLC levels. All response categories require 2 consecutive assessments made at any time before the institution of any new therapy; all categories also require no known evidence of progressive or new bone lesions or extramedullary plasmacytomas if radiographic studies were performed. Radiographic studies are not required to satisfy these response requirements. Bone marrow assessments do not need to be confirmed. Each category, except for stable disease, will be considered unconfirmed until the confirmatory test is performed. The date of the initial test is considered as the date of response for evaluation of time dependent outcomes such as duration of response.

c All recommendations regarding clinical uses relating to serum FLC levels or FLC ratio are based on results obtained with the validated Freelite test (Binding Site, Birmingham, UK).

d Presence/absence of clonal cells on immunohistochemistry is based upon the  $\kappa/\lambda/L$  ratio. An abnormal  $\kappa/\lambda$  ratio by immunohistochemistry requires a minimum of 100 plasma cells for analysis. An abnormal ratio reflecting presence of an abnormal clone is  $\kappa/\lambda$  of  $> 4:1$  or  $< 1:2$ .

e Plasmacytoma measurements should be taken from the CT portion of the PET/CT, or MRI scans, or dedicated CT scans where applicable. For patients with only skin involvement, skin lesions should be measured with a ruler. Measurement of tumor size will be determined by the SPD.

f Positive immunofixation alone in a patient previously classified as achieving a CR will not be considered progression. For purposes of calculating time to progression and PFS, patients who have achieved a CR and are MRD-negative should be evaluated using criteria listed for progressive disease. Criteria for relapse from a CR or relapse from MRD should be used only when calculating disease-free survival.

g In the case where a value is felt to be a spurious result per physician discretion (eg, a possible laboratory error), that value will not be considered when determining the lowest value.

h Sustained MRD negativity when reported should also annotate the method used (eg, sustained flow MRD-negative, sustained sequencing MRD-negative).

i DNA sequencing assay on BM aspirate should use a validated assay such as LymphoSIGHT (Sequentia).

j Criteria used by Zamagni and colleagues, and expert panel (IMPetUs; Italian Myeloma criteria for PET Use). Baseline positive lesions were identified by presence of focal areas of increased uptake within bones, with or without any underlying lesion identified by CT and present on at least 2 consecutive slices.

Alternatively, an  $SUV_{max} = 2.5$  within osteolytic CT areas  $> 1$  cm in size, or  $SUV_{max} = 1.5$  within osteolytic CT areas  $\leq 1$  cm in size were considered positive. Imaging should be performed once MRD negativity is determined by NGS.

Source: International Myeloma Working Group consensus criteria for response and minimal residual disease assessment in MM (Kumar et al, 2016); modified for protocol purposes

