**4. Objectives, Endpoints and Hypotheses**

**4.1 Objectives and Endpoints**

Objectives	Endpoints
Phase 1b	
Primary	

 
Establish the safety and tolerability of AMG 420 at dose levels of 400 µg/day and 600 µg/day in subjects with relapsed and/or refractory multiple myeloma (RRMM)
 
	
 
Dose-limiting toxicities (DLTs), treatment-emergent adverse events, treatment-related adverse events, and changes in vital signs, electrocardiograms (ECGs), and clinical laboratory tests
 

Key Secondary	

 
Estimate overall response rate (ORR) and duration of response (DOR) of AMG 420 in subjects with RRMM
 
	
 
ORR
 
DOR
 

 
Evaluate the rate of minimal residual disease (MRD)-negativity at the time of CR
 
	
 
MRD negativity at the time of CR
 

Secondary	

 
Establish the safety and tolerability of AMG 420 in subjects with extramedullary relapsed multiple myeloma
 
	
 
DLTs, treatment-emergent adverse events, treatment-related adverse events, and changes in vital signs, ECGs, and clinical laboratory tests
 

 
Characterize the pharmacokinetics (PK) of AMG 420 when administered as 4-week continuous intravenous (cIV) infusion
 
	
 
AMG 420 PK parameters including, but not limited to, half-life (<math>t_{1/2}</math>), clearance, and apparent <math>C_{ss}</math>
 

Objectives	Endpoints
Secondary	

• Evaluate other measures of anti-myeloma activity of AMG 420 in subjects with RRMM:

– Time to response

– Progression-free survival (PFS)

– Overall survival (OS)

– Best overall response (BOR)

	

• Efficacy parameters according to International Myeloma Working Group (IMWG) response criteria, per investigator assessment:

– Time to response

– PFS

– OS

– BOR

Objectives	Endpoints
Exploratory	

---

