#### **7.1.1.3 MRD-based Extended Treatment-free Interval**

The **treatment-free** interval may be increased as follows:

- Up to 4 weeks in subjects who attain MRD-negative disease status at 6 months from enrollment (based on all appropriate assessments to fulfill IMWG criteria),
- Up to 8 weeks in subjects who remain in MRD-negative disease status at 12 months from enrollment. Treatment will continue until progression or at the discretion of the investigator, can be discontinued at 24 months if subjects remains in complete remission.

**The treatment free interval may be decreased to the initial treatment free interval of 2 weeks at the discretion of the investigator upon informing the sponsor. Reinstatement of the treatment free interval at the cadence prior to the decrease is not permitted.**

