Time to response applies for subjects who achieved best overall response of PR, VGPR, CR or sCR. Time to response is calculated as the number of months (one month = 30.4 days) from the first administration of AMG 420 to the first objective assessment of response (ie, date of the first detection of response) as per IMWG-URC.

TTR (in months) = (Date of objective response – Date of first dose + 1)/30.4

MRD Negativity (MRD-)

MRD- is defined as a response of CR or sCR accompanied by any of the following types of MRD negativity.

- Sustained MRD-
- Sequencing MRD-
- Imaging plus MRD-

Subjects who do not experience a MRD negativity or do not have any evaluable follow-up assessments will be regarded as MRD non-responders.

Progression-free survival (PFS)

Progression free survival (PFS) is defined as number of months between start of treatment and first evidence of documented disease progression or death (due to any cause), whichever occurs first.

PFS (in months) = (Earliest date of disease progression, death, censor – Date of first dose + 1)/30.4

Progression-free survival will be right-censored for subjects who meet one of the following conditions: 1) no post baseline disease assessments, 2) non-protocol systemic anticancer treatment started before documentation of PD or death, 3) death or disease progression after more than 1 missed disease assessment visit or 4) alive and does not have documentation of PD before a data analysis cutoff date. For such subjects, the

primary analysis of PFS will be right-censored according to the conventions described in [Table 2](#).

Table 2. Conventions for Censoring for PFS and DOR

Situation	Date of Progression or Censoring	Outcome
No post baseline disease assessments**	Date of first dose	Censored
New anticancer therapy started before documentation of PD or death	Date of last evaluable disease assessment prior to start of new anticancer therapy	Censored
Death or PD immediately after more than 1 consecutively missed disease assessment visit*	Date of last evaluable disease assessment visit before the first missed visit	Censored
Alive and without PD documentation (including lost to follow-up without PD)	Date of last evaluable disease assessment	Censored
Death or PD between planned disease assessments	Date of death or first disease assessment showing PD, whichever occurs first	Progressed
Death before first disease assessment	Date of death	Progressed

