9.5.1.3 MRD Negativity at CR

MRD negativity analysis will be performed for all subjects included in the safety analysis set. Number of MRD[-] responders at CR along with exact 2-sided 95% will be provided by using Clopper & Pearson method

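### Protocol Appendix 8 states the sequencing threshold for MRD negativity backwards, so the definition behind a key secondary endpoint contradicts itself

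*Protocol*

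**What the plan says.** The MRD part of the response criteria table in Protocol Section 12.8 (Appendix 8) has a row for sequencing MRD negativity. Its condition is "Absence of clonal plasma cells by NGS on BM aspirate". The same sentence then explains what counts as a clone: "presence of a clone is defined as less than 2 identical sequencing reads". It ends with a required minimum sensitivity of 1 in 10^5 nucleated cells.

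The other two MRD rows in that table build on this one. Sustained negativity needs "MRD negativity in the marrow (NGS) and by imaging as defined below". The imaging-plus type needs "MRD negativity as defined by NGS plus disappearance of every area of increased tracer uptake".

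MRD negativity at the time of CR is a key secondary endpoint in Protocol Section 4.1 and SAP Section 2.1. SAP Section 5 gives its analysis definition: "MRD- is defined as a response of CR or sCR accompanied by any of the following types of MRD negativity". It then names the sustained, sequencing and imaging-plus types. Subjects who do not reach MRD negativity, or who have no evaluable follow-up assessment, count as MRD non-responders. SAP Section 9.5.1.3 sets the population: "MRD negativity analysis will be performed for all subjects included in the safety analysis set", with an exact Clopper-Pearson interval.

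MRD status has two further uses. Protocol Section 7.1.1.3 allows a longer treatment-free interval "in subjects who attain MRD-negative disease status at 6 months from enrollment", with a further provision at 12 months. Protocol Section 10.4.2.2 summarises the extended interval among subjects eligible by MRD-negative CR.

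**The concern.** The row states a condition (no clone) and then a read-count rule for the opposite state (clone present). The inequality in that rule points the wrong way. A sample with no matching reads would count as containing a clone, and a sample with 100 matching reads would count as free of one.

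This is the only read threshold visible in either document. The footnotes to the table do not correct it: footnote a deals with confirmation, footnote h with annotating the method, and footnote i asks for a validated assay without giving a threshold. The SAP names the types of negativity but gives no threshold.

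At stake is the operational definition of a key secondary endpoint, and of the MRD status on which the treatment-free-interval text and its summary rely.

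**Working it through.** There is no stated figure to reproduce. The check has three steps.

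**1. Classification by read count.** Let r be the number of identical reads, and let MRD-negative mean that no clone is present. As written, a clone is present if r < 2. With the inequality turned round, a clone is present if r ≥ 2.

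| r | As written | Inequality turned round |
|---|---|---|
| 0 | positive | negative |
| 1 | positive | negative |
| 2 | negative | positive |
| 5 | negative | positive |
| 100 | negative | positive |

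The two rules disagree at every read count.

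**2. Is there a route to the endpoint that avoids the row?** SAP Section 5 accepts any of three types. Sequencing negativity alone is enough, and the sustained and imaging-plus types both require NGS negativity as well. The endpoint therefore reduces to CR or sCR with an NGS-negative marrow. No route avoids the row.

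**3. Effect on the reported rate if the text were applied literally.** Let N be the size of the analysis set, m the number in CR or sCR with an NGS result, and k the number of those with fewer than 2 reads.

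- Intended rate: k/N.
- Literal rate: (m − k)/N.
- The other N − m subjects are non-responders under both rules, so the literal rate is not 1 − k/N.
- If k happens to equal m/2, the two rates coincide, although every tested subject is misclassified.

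Illustrations, with exact 95% intervals (the SAP's method):

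- *Assumed cohort.* N = 10, m = 5, k = 4. Intended: 4/10 (12.2% to 73.8%). Literal: (5 − 4)/10 = 1/10 (0.3% to 44.5%). A simple complement would have been 6/10.
- *First-in-human counts.* Protocol Section 3.2.2.4 reports 35 subjects, with 6 CRs of which 4 were MRD-negative. Assume that all six had an NGS result and that the remaining two were positive. Among CRs, 4/6 (66.7%, 22.3% to 95.7%) becomes 2/6 (33.3%, 4.3% to 77.7%). Over all 35, 4/35 (11.4%, 3.2% to 26.7%) becomes 2/35 (5.7%, 0.7% to 19.2%).

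The second illustration only gives scale. It comes from a different study, and this protocol says neither how MRD was measured there nor whether the two other CRs were tested.

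**The case against.** The strongest reply is that the intended meaning is plain. The row is headed as a negativity criterion, its condition is absence of clonal cells, and a sensitivity floor makes sense only if negativity means failing to detect a clone. An experienced reader will see a slip rather than a second workable rule. That is fair, and it is why this is an internal contradiction and not a design choice.

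A second reply is that nobody at the site or in the analysis is asked to count reads. Protocol Section 9.2.2.7 has MRD measured centrally, Table 12-1 lists it under the central laboratory, and the SAP can work from the reported call. This also stands. A reader might infer that the endpoint will be reported in reverse, but the documents do not support that: the description of the central method is blacked out, and the laboratory's own positivity rule may well prevent the error. Equally, nothing visible shows that it does.

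A reader might also infer that treatment-free-interval decisions would be reversed. Section 7.1.1.3 is permissive, refers to the IMWG criteria in general and cites no read count. A reversal would need the laboratory call itself to be inverted, which is not shown.

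Finally, the wording may have been carried over from the cited consensus criteria. That cannot be checked here. The table's source note says that it was adapted for this protocol, and the sentence contradicts itself whatever its origin.

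**Conclusion.** The threshold is wrong as written. It contradicts the condition in its own sentence, nothing visible in the protocol or SAP corrects it, and every accepted type of MRD negativity depends on it.

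Its demonstrated size is limited. Under literal use, k of m tested CR/sCR subjects becomes m − k of m. The safety-set rate shifts from k/N to (m − k)/N. A reader might infer that the whole reported rate becomes one minus itself. It does not, because subjects without CR, or without an evaluable result, stay non-responders under either rule.

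Whether any subject would in fact be misclassified depends on a laboratory rule that is not visible. If the laboratory calls MRD in the conventional way, the harm is a mismatch: the reported key secondary endpoint would contradict its protocol definition. The missing threshold in the SAP is not a separate defect, since the SAP defines MRD negativity by type and can rely on the laboratory call.

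**What to change.** Correct the sequencing row in Appendix 8 so that absence of a clone means fewer than 2 identical reads, and presence means 2 or more. Check this against the central laboratory's validated positivity rule before issuing it.

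Optionally, have the SAP Section 5 definition refer to the corrected row or to the central laboratory's MRD call.

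Reconcile Protocol Sections 7.1.1.3 and 10.4.2.2, which use MRD status, with the corrected definition. No view is taken here on the treatment-free-interval rule itself.

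The cost is one phrase in the protocol, one query to the laboratory and, if wanted, one cross-reference in the SAP. No new data or procedures are needed.

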## 12.9 Appendix 9. Clarification on Eligibility Criteria: Definition of Relapsed or Refractory Disease and Line of Treatment

**Refractory multiple myeloma** is defined as disease that is nonresponsive while on primary or salvage therapy, or progresses within 60 days of last therapy: Nonresponsive disease is defined as either failure to achieve minimal response (MR). There are 2 categories of refractory multiple myeloma:

- **Relapsed and refractory multiple myeloma.** Relapsed and refractory multiple myeloma is defined as disease that is nonresponsive while on salvage therapy, or progresses within 60 days of last therapy in patients who have achieved MR or better at some point previously before then progressing in their disease course.
- **Primary refractory multiple myeloma.** Primary refractory multiple myeloma is defined as disease that is nonresponsive in patients who have never achieved a MR or better with any therapy. It includes patients who never achieve MR or better in whom there is no significant change in M-protein and no evidence of clinical progression as well as primary refractory, PD where patients meet criteria for true PD.

Relapsed multiple myeloma is defined as previously treated multiple myeloma that progresses and requires the initiation of salvage therapy but does not meet criteria for either “primary refractory myeloma” or “relapsed-and-refractory multiple myeloma” categories.

A line of therapy is defined as 1 or more cycles of a planned treatment program. This may consist of 1 or more planned cycles of single-agent therapy or combination therapy, as well as a sequence of treatments administered in a planned manner.

For example, a planned treatment approach of induction therapy followed by autologous stem cell transplantation, followed by maintenance is considered 1 line of therapy ([Rajkumar et al, 2011](#)).

